1.2 BACKGROUND

1.2.1 Goals of First Aid

The ERC First Aid Writing Group (ERCFAWG) stated the goals of first aid to include life preservation, suffering alleviation, preventing further illness or injury and

promoting recovery [1]. They equally agreed that the process can be undertaken or initiated by “anyone in any situation” including oneself. In their guidelines, it was agreed upon that, first aid training at EVERY level should contain pertinent principles which include: Identifying, evaluating, and determining the urgency of first aid requirements, administering care with suitable skills and acknowledging constraints/limitations and requesting further assistance when necessary, including activating the emergency medical services (EMS) system or seeking other medical aid [1]. These principles therefore include individuals or groups of individuals irrespective of age, gender, race or other socioeconomic or demographic characteristics. As such, children are not left out. This is why, in most countries of the Global North, first aid is included in the educational curriculum from a tender age, as young as kindergarten [4,5]. Several countries have succeeded in lowering morbidity and mortality by developing a strong and resilient emergency medical service [6,7] which includes lay-first responders (LFR). This has begun trickling into sub-Saharan Africa [8]. However, the focus is on training adult lay-first responders, particularly regarding road traffic crashes as timely transportation to a care service is essential for favourable outcomes. Children can also save lives and training children on first aid has proven effective in some pilot studies carried out in India and other African settings [9]. It is helpful when planning to train individuals on FA that trained bystanders act promptly and appropriately in the face of emergencies needing a first aid response compared to those that are untrained. [10].

However, it is important to consider the self-efficacy of performing a delicate act such as FA and there needs to be a change of culture and mindset of people within a given sphere or community. Habits cultivated, knowledge refreshers, and application of certain practices over time increase people’s self-confidence and efficacy in performing

such activities [11].

As such, we not only want to improve the knowledge of adults about first aid, but we want to build a culture of trained bystanders who are physically and psychologically equipped to alleviate emergencies in the face or at least call for help. This, we believe needs to be inculcated from a tender age so that the instinct to help alleviate suffering and/or prevent complications from emergencies, particularly trauma/ injury emergencies stays in the subconscious of individuals and develops over time to save lives better. For this reason, we want to use the full developmental potential of our children in the lower secondary schools to begin this initiative.

To achieve our objectives, we must consider some key principles of first aid should adhere to medical standards and be supported by the most reliable scientific findings, should be accessible to all, with universal participation in learning these skills, encouraging supportive actions should be a priority for all individuals and the extent of first aid and supportive actions can differ and might be impacted by environmental, resource, training, and regulatory elements [1].

These principles have further emphasized the need to include children or students in our cohort of trained bystanders or LFRs for our communities, particularly our schools.

1.2.2 Benefits of First Aid Training in Schools

Integrating first aid training into the school curriculum in Sub-Saharan Africa, including Cameroon is crucial for equipping young people with life-saving skills, addressing health challenges, and contributing to overall educational and societal well-being specifically via the development of, firstly,

Vital Life-Saving Skills as responding to medical emergencies, and potentially saving lives in their settings. First aid training provides highly sought-after skills that can be

crucial in emergencies and later in life [12]. Neglecting the importance of first aid could be to the detriment of society which is a similar situation in our country.

Secondly, Risk Evaluation abilities especially since young people are unable to assess risk evaluation in the same way as adults [13][12].

Thirdly, first-aid training decreases disease and injury burden which is a cost-effective way to decrease the burden of disease and injury, particularly in low- and middle-income countries [14].

Fourthly, access to quality education is key to social mobility and poverty reduction, and incorporating first aid training into the curriculum of young children can contribute to this aspect of education [15].

Also, SSA has a high rate of Education Exclusion or inequality. This can be addressed by incorporating first aid training in schools, thus providing additional skills and knowledge to the students or pupils [15].

Fourthly, access to quality education is key to social mobility and poverty reduction, and incorporating first aid training into the curriculum of young children can contribute to this aspect of education [15].

Also, SSA has a high rate of Education Exclusion or inequality. This can be addressed by incorporating first aid training in schools, thus providing additional skills and knowledge to the students or pupils [15].

Lastly, positive impact on Education Recovery as there is a persistent teacher gap in SSA. Integrating FA training in the educational system, can contribute to the wellbeing of students overall. Thereby, support the education recovery efforts in the region [16].

Since trauma and injury incidents are common in Africa, and the lack of adequate first

aid training often leads to adverse outcomes, this study seeks to identify the challenges in implementing first aid training, evaluate the effectiveness of such training, and assess the overall impact on the well-being of school children and the community.

1.3 PROBLEM STATEMENT

The lack of formal first aid training or its emphasis in the curriculum of most medical schools makes one understand the degree of the gap in knowledge, attitudes and practices in the regular university not to talk of the high, secondary schools and within the communities [18]. This emphasizes the need to raise the awareness of communities of individuals including school children and teachers on FA [19]. As such, it is important for school children and teachers to learn the most basic FA skills as they are often first on the incident or accident scenes within the campuses. This cannot be overstressed as the school is the place where students and teachers spend most of their day. It could be assumed that all schools have dispensaries or infirmaries but in our setting, only a few are effectively functional. According to a report by the World Health Organization (WHO), only four countries in Africa meet the recommended density of health workers per 1000 people, indicating a severe shortage of healthcare professionals on the continent [8,9]. This may translate to the situation of dispensaries or infirmaries in schools in sub-Saharan Africa and Cameroon.

Although there is an improvement in school enrolment over the years in schools in sub-Saharan Africa including Cameroon, there is little or no evidence of the same

improvement in functional dispensaries or infirmaries in the increasing numbers of schools too. Nor is there information on a strategized referral system from the school setting to the health facility despite the need for collaboration between schools and proximate health facilities. Moreover, in the advent of an injury in school premises, there may be delays in referral to appropriate facilities because of undefined standard operating procedures and knowledge deficits with no prior alleviation of the immediate danger to the victim.

Thus the importance of introducing the YoFA program with refresher courses over time in which the people get better at the skill and some may even get into formal training in future.

1.4 RATIONALE OF THE STUDY

Since the most common first aid needs will arise from falls, cuts/wounds, during play periods, compared to other emergencies like choking or syncope, it is essential to focus more on bleeding injuries/trauma first aid since they are more visible trauma injuries compared to strains, sprains, fractures, among others. Furthermore, safe and timely referral (while raising awareness on the need and importance of the general aspects of FA) to the closest HF is essential to maximize the golden hour and avert adverse preventable outcomes.

Since it is a pioneer lay First responder kids' program, we will not focus on Advanced Trauma Life Support as these are not medical professionals although the training program will have a great role in honouring the 'golden hour' in trauma/injury. As such starting with life threatening bleeds FA which have proven effective in some countries is a worthwhile beginning.

Despite the numerous factors contributing to life-threatening bleeds (LTB), such as road

traffic crashes (RTCs) and acts of violence, the data on LTB-related fatalities indicates a need for enhanced point-of-injury interventions to effectively prevent LTB [20]. As such, we will apply an adaptation of the “Stop the bleed” and “Do something” programs in our context in Cameroon to help curb complications from emergencies with a special focus on LTBs in the community. Since innovations need time to be a culture among a people, it is essential to begin in small scale and among a population that can grow with the desired behaviour change or culture. One more reason why early secondary school students as pioneers for this program in Cameroon is because they do not have a lot of financial responsibilities and may not be focused on any monetary reward. What will be left to do if the uptake and application is favourable will be to ensure spread to other schools and ensure sustainability.

1.5 RESEARCH QUESTIONS

1. What community perceptions exist about children learning and/or using FA skills within the school setting or thereabouts?
2. What is the level of Knowledge, the attitudes and practices (KAP) of early secondary school children (SSC) on injury/trauma FA?
3. How efficacious and usable is an injury/trauma Young First Aiders' (YoFA) training program to early SSC and the community?
4. What are the perceived barriers/challenges and benefits of the YoFA program in schools and the community?

1.6 RESEARCH OBJECTIVES

1.6.1 General Objective

1. To gain insights into the perceptions and barriers surrounding a Young First Aiders' (YoFA) training program on trauma/injury first aid in both the school setting and the

community in the Fako Division.

2. To assess and measurably improve KAP of SSC on trauma/injury FA using the YoFA training program in Fako Division.

1.6.2 Specific Objectives

1. To understand the perspectives of stakeholders (school teachers, administrators, parents, community leaders and students) on a school-based FA training (YoFA) program among SSC.

Hypothesis 1: The perspectives of stakeholders like school administrators, teachers, parents, community leaders, and school children needs to be understood to design a comprehensive YoFA program

2. To assess school children's Knowledge, Attitudes (willingness to) and Practices (self-efficacy) (KAP) on trauma/injury FA via the built YoFA training to stop LTBs.

Hypothesis 2: School children have limited knowledge, self-efficacy and practices regarding trauma/injury FA

3. To evaluate the effectiveness and usability of the YoFA training program for SSC to respond to LTBs safely and promptly in their environs.

Hypothesis 3: The YoFA training Program is effective in improving the KAP of SSC and it is usable within the school and community setting.

4. To determine the barriers associated with implementing the YoFA program among early SSC in the Fako Division.

Hypothesis 4: There exist some barrier/challenges in implementing a YoFA training

program in secondary schools.

CHAPTER TWO

LITERATURE REVIEW

It is important to understand some aspects regarding first aid training for children in schools. Here, we will be highlighting the relevance of Advanced Trauma Life Support concepts, the injury burden among school children, the qualifications of potential educators, and the appropriateness of school-based training. There is a clear consensus on the necessity and benefits of teaching first aid in schools, as it equips children with essential life skills, enhances their confidence, and promotes a safer environment. Future research should focus on developing effective training programs tailored to this age group, considering the emotional aspects of learning and the varied contexts in which children may need to apply their skills particularly in our setting.

First aid training is an essential aspect of emergency preparedness, particularly for children aged 10 to 14 years. This age group is increasingly exposed to various risks, both in schools and everyday life. Here, we will explore four key areas related to first aid training for children: the concept of Advanced Trauma Life Support (ATLS), the injury burden among school children, potential educators of first aid, and the appropriateness of implementing first aid training in schools.

Advanced Trauma Life Support

Advanced Trauma Life Support (ATLS) is a systematic approach to the management of trauma patients, focusing on rapid assessment and treatment of life-threatening conditions [3]. The ATLS course teaches a systematic and concise approach to the early care of trauma patients, emphasizing the immediate management of injured patients and the rapid assessment of life-threatening conditions [3].

Additionally, it is recognized as a foundation of care for injured patients, providing a

common language and approach for trauma management. The program is designed to ensure that life-threatening injuries are identified and treated promptly, which is crucial in trauma care [10]. This systematic approach is essential for improving trauma outcomes and is widely adopted in emergency departments around the world [3,11].

While ATLS is primarily designed for healthcare professionals, its principles can be adapted for educational purposes to teach children basic life-saving skills [2]. Research by Heller et al. (2020) suggests that introducing simplified versions of ATLS concepts can enhance children's understanding of prioritizing care in emergency situations.[2] By familiarizing children with the basic principles of trauma management, such as airway management, breathing, and circulation, they can better respond to traumatic incidents that may occur in their environments. However, it is crucial to tailor ATLS concepts to be age-appropriate. Studies indicate that children aged 10 to 14 are capable of understanding basic trauma care principles when presented in an engaging format [12]. This adaptation can include role-playing scenarios and interactive demonstrations, making the training more relatable and practical for young learners.

Injury Burden Among School Children

The injury burden among school children is significant, with various studies highlighting the prevalence and impact of injuries in this age group. According to the World Health Organization (WHO), unintentional injuries are a leading cause of morbidity and mortality among children aged 10 to 14 [13,14]. Common injuries include falls, sports-related injuries, and accidents during transportation. The high incidence of injuries underscores the necessity for effective first aid training programs in schools, which can equip children with the skills needed to respond to such incidents [15].A study by Tse et al. (2023) found that children who received first aid training were more likely to recognize and respond appropriately to injuries among their peers,

thus reducing the severity of injuries and improving outcome [16]. This highlights the critical role of first aid training in mitigating the injury burden and promoting a safer school environment.

Who Can Teach Children First Aid?

The effectiveness of first aid training is heavily influenced by the qualifications of the instructors. Potential educators include trained teachers, parents, healthcare professionals, and peers.[17] Research by Baker et al. (2021) indicates that trained teachers are often the most effective facilitators, as they can integrate first aid training into the school curriculum and ensure that the material is delivered consistently. Parents also play a vital role in reinforcing first aid knowledge at home. A study by Alshehhi and El-Aidie (2023) found that parental involvement in first aid education significantly enhances children's retention of skills [18]. Additionally, peer-led training programs can foster a supportive learning environment, where children feel more comfortable practicing skills with friends [19]. However, the effectiveness of peer training may depend on the peers' knowledge and confidence in first aid skills.

Is It Appropriate to Train Children in First Aid in Schools?

The appropriateness of training children in first aid within school settings has been a topic of considerable debate. Advocates argue that early education in first aid is essential, given the prevalence of injuries and emergencies in school environments. Training not only empowers children to act in emergencies but also promotes a culture of safety and responsibility [20,21]. Conversely, some critics raise concerns about the emotional and psychological readiness of children to handle traumatic situations. Research suggests that while children can learn first aid skills, care must be taken to ensure training is age-appropriate and does not induce fear or anxiety about emergencies. Schools should adopt a balanced approach that emphasizes skill

acquisition while providing emotional support and context, ensuring that children feel prepared rather than overwhelmed [15,17].

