3.3.1 Qualitative Part

Discussions or interviews on perspectives of individuals and groups of individuals regarding the acceptability and usability of FA-trained kids within the school and in the community. It will also seek to understand their thoughts on incorporating an FA training program within the school curriculum. It will be conducted with key stakeholders, including school administrators, and community leaders as well as students of the school.

It will precede the qualitative part and include Focused group discussions (FGDs), in-depth interviews of certain community and administrative stakeholders within the school and observations of scenarios.

3.3.2 Quantitative Part:

The quantitative aspect will involve administering questionnaires to students to assess their knowledge, attitudes (confidence), and practices (utilisation/usability) of FA trauma/injury skills before and after their training. This will focus mostly on staying safe, calling for help and stopping a life-threatening bleed. The intervention will include training the intervention group in reasonable clusters on the same subject matter and assessing the change in KAPs before and after the intervention. It will also include scenarios to test the efficacy of participants in carrying out the First Aid Act.

PERIOD OF STUDY

The study will be a 10-month study from September 2024 to July 2025 including administrative and ethical clearance needed.

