3.8 DATA COLLECTION TOOLS

A) Questionnaire

**Pre- and Post-Implementation of a Young First Aiders (YoFA) Training
Program Amongst Early Secondary School Children on Injury and Trauma
First Aid in Fako Division.**

Health District _____
Secondary School _____

Date: _____
Class: _____

A) QUESTIONNAIRE

Section 1

Please answer the questions below by **ENCIRCLING OR WRITING** the right answer you think is correct. If you do not know an answer, please select the answer you think is correct.

1. Gender	YES	or	NO
2. Age (in years):	_____		
3. Parents' Occupation:	Father _____ Mother _____		
4. Do you have access to a mobile phone all the time?	YES	or	NO
5. Have you heard the words First Aid?	YES	or	NO
6. Have you ever seen a traumatic injury? (A traumatic injury is an injury you sustain when something outside your body causes you to lose function or render you unable to use part or all of your body because of pain, bleeding or the because it is very serious)	YES	or	NO
7. A) Have you ever received any training in First Aid (formal or informal)?	YES	or	NO
B) If yes, briefly describe the training (where was it, what did you learn? How long ago was it?)			
Where? _____			
How long ago?			

 a) < 6months ago b) 6 to less than 12 months ago c) 1 to 3 years ago d) >3 years ago 			
What you learnt? _____			
<hr/>			
8. Have you ever seen someone bleeding and tried to stop that bleed yourself at home, school, marketplace, or anywhere else?	YES	or	NO
B) How many times has that happened? (Choose one)			

 a) Never b) Just once c) 2 to 5 times d) >5 times 			

C) What did you do to stop the bleeding? _____ **YES** or **NO**

D) Did it work? **YES** or **NO**

9. **A) Do you remember watching other people do this in the past?** **YES** or **NO**
B) Have you ever watched someone else offer such help in question 5? **YES** or **NO**

10. **If you find someone bleeding today,** **YES** or **NO**

A) Will you help them?

B) If 'no', why will you not help?

- I don't know what to do
- I am afraid I will make it worse
- I am afraid I will get into trouble
- I am afraid of blood
- Other reason _____

C) If 'yes', why will you help? _____

D) What steps will you take to help if 'yes'?

- Help by putting in toothpaste
- Help by applying pressure on the wound
- I will not help
- I will call an elderly person.

[figure not shown]
B) If you would not help, what makes you not want to help?

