3.11 DATA ANALYSIS PLAN

A difference-in-difference analysis would be done to assess the change in KAPs before and after the intervention in. The posttest would be done immediately after the 4 days of training for each pool and 3 months after the training to assess the need for refresher course planning.

The exposure variables include training on LTBs from injury first aid and the use of these services by the trained students (e.g., the number of persons assisted or referred during the follow-up period of the training).

We will analyze survey data using R Software with a combination of descriptive statistics and parametric and non-parametric tests to establish statistically significant differences between pre- and post-test results and between the intervention and control groups.

Table 7: Objectives and their Indicators

Objective	Activities/process	Data collection tools	Data Source	Indicators
1. To understand the perspectives of stakeholders on YoFA training program among SSC	- In-depth interviews	-In-depth interview guides	School teachers, administrators, parents, community leaders and students	
2. To assess school children's KAP (willingness and self-efficacy on trauma/injury FA via the built YoFA training to stop LTBs.	- survey	-Questionnaire	- students	- Obtain baseline KAP Scores
3. To evaluate the effectiveness and usability of the YoFA training program for SSC to respond to LTBs safely and promptly in their environs.	-Training following a specific STB and LFRs program -Training students on specific modules of LTB FA - Pre and post test -Simulation exercises	- Use adapted tools from the SBEAT - Questionnaires - Evaluation form with questions how? What was the situation?where, and how?	Stakeholders, teachers, parents, students	- Change in knowledge scores -At least 50% of stakeholders rate the program as good/ expectations met - 70% of students rate the program as good/expectations met - Number of children who made use of the FA skills taught
4. To determine the barriers associated with implementing the YoFA program among early SSC in the Fako Division.	- Interviews - Survey	-Interview guides - Questionnaires	- Stakeholders, - Teachers, students	- Perceived reasons and challenges that hinder FA training in schools.

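### Item 8, the only question on a pupil's own past first aid, joins seeing a bleed with acting on it, so the past-practice part of Hypothesis 2 mixes opportunity with conduct

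*Protocol*

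**What the plan says.** Research question 2 (protocol, section 1.5) asks: "What is the level of Knowledge, the attitudes and practices (KAP) of early secondary school children (SSC) on injury/trauma FA". Hypothesis 2 (section 1.6.2) answers in advance: "School children have limited knowledge, self-efficacy and practices regarding trauma/injury FA". It names practices as a separate element next to knowledge and self-efficacy.

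The protocol describes practices in two ways. Objective 2 in section 1.6.2 has "Attitudes (willingness to) and Practices (self-efficacy) (KAP", which equates them with self-efficacy. Section 3.3.2 (Quantitative Part) has "attitudes (confidence), and practices (utilisation/usability", which points to actual use of the skills. Table 7 in section 3.11 assigns objective 2 to the questionnaire and gives as its indicator "Obtain baseline KAP Scores".

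In the questionnaire (section 3.8), the question on the pupil's own past action is item 8: "Have you ever seen someone bleeding and tried to stop that bleed yourself at home, school, marketplace, or anywhere else", with a single YES or NO. Item 8B follows with "How many times has that happened? (Choose one" and runs from 'Never' to more than five times. Items 8C and 8D ask what was done and whether it worked. Item 6 asks separately: "Have you ever seen a traumatic injury", with a printed explanation that turns on losing the use of part or all of the body through pain, bleeding or seriousness.

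**The concern.** Item 8 puts two conditions under one answer: the pupil met a bleeding person, and the pupil personally tried to stop the bleed. A NO is the correct answer for a child who never had the occasion and also for one who had it and did nothing. It is probably also the answer of a child who fetched an adult, because the item asks about the pupil's own attempt. 'Never' in 8B refers back to the same joint statement, and 8C and 8D concern only pupils who acted.

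At stake is how the baseline figure on past practice is read. A low share of YES answers is compatible with children who do not act, which is a training need, and with children who had little to act on. Two schools with identical conduct but different exposure would show different item 8 figures. An analysis plan cannot repair this later, because nobody will have asked the pupils about exposure to bleeding.

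**Working it through.** **The plan's own figure.** The protocol gives no figure for past practice, for exposure to bleeding or for conduct among the exposed. Its one calculation, 58 per group for 0.50 against 0.75 (section 3.5), reproduces but is not linked to item 8.

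**Can another printed item (section 3.8) supply the exposure?**
- Item 6 asks about traumatic injury. Its explanation mentions bleeding as one possible cause of lost function, but a YES can refer to an injury without bleeding, and a pupil who has seen only ordinary cuts can answer NO. Section 1.4 names falls and cuts at play among the most common first aid needs.
- Items 9A and 9B ask about watching other people help. A YES suggests that a bleed was seen; a NO does not show that none was.
- Item 10 asks what the pupil would do today, which is intention.
- Items 13 to 37 test knowledge and the right action in described situations.

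Crossing item 6 with item 8 gives three informative groups. Item 8 YES means exposed and acted. Item 8 NO with item 6 YES means some function-limiting injury was seen, with or without bleeding. Item 8 NO with item 6 NO means no such injury was seen, but possibly a lesser bleed. The last two groups each still mix exposed and unexposed pupils, so the separation is partial.

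**Illustration of size.** Let e be the share who have ever met a bleeding person and h the share of those who personally tried to stop the bleed. Both are assumptions.
- Share answering YES = e × h
- Share answering NO = 1 − e × h
- Share of NO answers due only to no opportunity = (1 − e) / (1 − e × h)

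Each cell gives the share answering NO, then the part of those NO answers due to no opportunity.

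| e | h = 0.3 | h = 0.5 | h = 0.8 |
|---|---|---|---|
| 0.2 | 94%; 85% | 90%; 89% | 84%; 95% |
| 0.4 | 88%; 68% | 80%; 75% | 68%; 88% |
| 0.6 | 82%; 49% | 70%; 57% | 52%; 77% |
| 0.8 | 76%; 26% | 60%; 33% | 36%; 56% |
| 1.0 | 70%; 0% | 50%; 0% | 20%; 0% |

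Example for e = 0.6, h = 0.5: NO = 1 − 0.30 = 0.70, and (1 − 0.6) / 0.70 = 0.57. For e from 0.2 to 0.8, the share answering NO runs from 36% to 94%, and 26% to 95% of those answers reflect no opportunity. At e = 1 the ambiguity vanishes.

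**Price of conditioning.** Take the 140 pupils of Table 5 (70 + 70), treated as independent, with e = 0.6 and h = 0.5. The unconditional proportion is 0.30 with half-width 1.96 × √(0.30 × 0.70 / 140) = 0.076. The conditional one is 0.50 among 0.6 × 140 = 84 pupils, with half-width 1.96 × √(0.50 × 0.50 / 84) = 0.107. The interval widens from about ±7.6 to ±10.7 percentage points.

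**The case against.** The strongest reply is that little depends on item 8. Hypothesis 2 is a descriptive baseline statement without a stated test. The outcome variables in section 3.7 are knowledge change, test scores, self-efficacy, response time and the number of pupils using the skills after training, and that last outcome is also documented by school visits and forms. Item 10 conditions on opportunity and records reasons for not helping, so it informs the training need. The expectations under Step 3 of section 3.6 list never having given first aid, for whatever reason, as one expected baseline state. On that reading the unconditional figure is a legitimate description. Finally, if nearly all pupils aged 10 to 14 have seen someone bleed, the problem is small.

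Most of this stands, and it limits the point. It does not make a NO to item 8 interpretable, and intention in item 10 is not past conduct.

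A reader might also infer more than the documents support:
- That Hypothesis 2 as a whole rests on this item. It does not: knowledge and self-efficacy have their own measures, and objective 2 itself glosses practices as self-efficacy.
- That lack of opportunity will be reported as lack of practice. The protocol fixes no practice score, denominator or cut-off for 'limited', so this cannot be read from it.
- That the comparison of the groups is biased because Table 1 shows more trauma in Tiko (average 1280.5) than in Buea (487.75). These are raw case counts that section 3.1 suspects of under-reporting; they do not measure what pupils have seen.

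**Conclusion.** The point holds in a limited form. Item 8 is the only printed question on the pupil's own past first aid, and its NO and 'Never' answers cannot separate no opportunity from no action. The past-practice part of research question 2 and of Hypothesis 2 is affected; the rest of Hypothesis 2, the sample size and the other listed outcomes are not shown to be. Existing items recover the distinction only in part.

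The effect could be negligible or could account for most NO answers, depending on exposure and conduct shares that the documents do not give; the table shows assumptions, not estimates. The conclusion assumes that practices include first aid actually given, as section 3.3.2 suggests and as the separate naming of self-efficacy in Hypothesis 2 implies. It is a moderate defect of the instrument, worth correcting because the correction is nearly free.

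**What to change.** Before the pretest, replace the stem of item 8 with two questions in every version of the questionnaire:
- 8(i): Have you ever seen someone bleeding? YES / NO.
- 8(ii): If yes, what did you do? Tried to stop the bleeding myself / called an adult or other help, or referred the person / nothing.

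The middle option of 8(ii) is needed because the success criteria under Step 3 of section 3.6 credit calling an adult, teacher or health facility, and referral. A plain YES or NO on stopping the bleed would score those pupils as inactive.

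Report practice among pupils answering yes to 8(i), next to the unconditional proportion among all pupils, which matches the baseline expectation in section 3.6. Report 8(i) by school. State in the protocol which meaning of practices Hypothesis 2 uses.

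The cost is one extra short question and, for the conditional figure, a smaller denominator with a somewhat wider interval. The unconditional figure loses nothing.
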